#### 13.1.2. Significance

A p-value less than or equal to 5% will be considered to be statistically significant.

#### 13.1.3. Analysis

Participants who have commenced the study treatment will be included in the analysis dataset. Reasons and frequency distribution of participants discontinued at Baseline will be reported. The analysis of efficacy variables such as subjective ratings will employ only scheduled and evaluable visits.

The analysis of safety variables such as adverse responses will include all visits, including all unscheduled visits.

Data will be summarised as means  $\pm$  standard deviations for variables measured on an interval scale and median  $\pm$  inter-quartile range for ordinal variables. Statistical tests will be employed to determine significant differences between between visits and  $p \leq 0.05$  will be considered statistically significant. Multiple comparisons will be adjusted using Bonferroni's correction. Commonly used tests of significance at each visit may include paired t-tests and group t-test for parametric data and Wilcoxon sign rank test and rank sum test for non-parametric data or repeated measures Analysis of Variance (ANOVA) for parametric data to determine differences between within-subject factors. Ranked variables will be analysed non-parametrically using Friedman's analysis of variance or Wilcoxon Signed Rank test to determine differences. Paired categorical variables will be compared using McNemar's test and grouped categorical variables will be analysed using Chi-Square tests.

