# 1. PROTOCOL SYNOPSIS

Table 1

Protocol Title	The effects of dietary supplementation with a combination of flaxseed oil, borage oil and fish oil omega-3 fatty acids on ocular comfort including symptoms of dry eye.	
Protocol ID Number	SOVS2016-045	
Trial Classification	Evaluation	
Investigator(s)/Site(s)	Eye Research Group @ SOVS The University of New South Wales Sydney, Australia	
Overall Duration of Trial	1 year	
Number of Trial Participants Planned	138	
Planned Start Date	February 2017	
Primary Objective	To investigate the efficacy of a nutraceutical formulation (combination of flaxseed oil, borage oil and fish oil omega-3 fatty acids) on ocular symptoms including dry eye, compared to a placebo control.	
Secondary Objective	To evaluate the safety of a nutraceutical formulation (combination of flaxseed oil, borage oil and fish oil omega-3 fatty acids) over a 3 month period.	
Primary Safety Variable(s)	Visual acuity Biomicroscopy: ocular redness, corneal and conjunctival staining	
Primary Efficacy/Performance Variable	Subjective symptom scores measured using OSDI, OCI and DEQ-5	
Experimental design	 Retrospective  Prospective  Single group  Multiple group  Parallel group  Cross over  Contralateral	 Single masked (Trial Participant)  Single masked (Investigator)  Double masked  Sponsor masked  Open label  Other

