### **6.1.6. Primary Endpoint**

Subjective ocular comfort and symptoms assessed using validated questionnaires.

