### **6.1.7. Secondary Endpoint(s)**

Non-invasive tear film break-up time, tear evaporation rate, tear meniscus height, tear volume and lipid layer thickness.

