#### 13.1.1. Number of Participants

138 participants will be recruited (69 in each group, which includes allowance for a 10% drop-out rate).

This sample size was calculated on the basis of detecting a difference in OSDI score of 10, with a standard deviation of 20, assuming an estimate of type 1 error  $\alpha = 0.05$  and power of 80% for a two tailed test. These values were obtained from Schiffman et. al. who demonstrated a mean difference in OSDI score of 10 between normal subjects and those with mild to moderate dry eye, with a standard deviation of up to 20.

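### Section 13.1.3 prescribes single-step Bonferroni, where Holm's step-down procedure controls the same error, never rejects less and sometimes rejects more (low severity)

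*Combined protocol and SAP*

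**What the plan says.** The only multiplicity rule is one sentence in section 13.1.3 (Analysis): "Multiple comparisons will be adjusted using Bonferroni's correction". It does not say which comparisons form the family or how many there are. The sentence before it reads in part "Statistical tests will be employed to determine significant differences between between visits". The sentence after it lists paired and two-group tests at each visit, and repeated-measures ANOVA for within-subject factors.

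Several sets of comparisons could be meant:

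- **Visits:** three scheduled visits (section 6), hence three pairwise contrasts per variable.
- **Primary endpoint:** section 6.1.6 gives "Subjective ocular comfort and symptoms assessed using validated questionnaires"; the synopsis (section 1) gives "Subjective symptom scores measured using OSDI, OCI and DEQ-5", which is three scales.
- **Secondary endpoints:** section 6.1.7 lists five measures, "Non-invasive tear film break-up time, tear evaporation rate, tear meniscus height, tear volume and lipid layer thickness".

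The general criterion in section 13.1.2 is "A p-value less than or equal to 5% will be considered to be statistically significant". The sample size in section 13.1.1 rests on "detecting a difference in OSDI score of 10, with a standard deviation of 20" with "power of 80% for a two tailed test". That is one comparison at unadjusted 0.05, and no power is stated for any other variable.

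**The concern.** Bonferroni holds every test in a family of m to 0.05/m, even after some of the hypotheses have been rejected. Holm relaxes the threshold as rejections accumulate and still keeps the family-wise error at 5% under any dependence between the tests. Where both are available from the same p-values, Bonferroni buys no extra error control in return for its stricter later thresholds.

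At stake is power for comparisons beyond the first rejection. The sample size makes no allowance for multiplicity, and the objective and hypothesis (sections 5.1 and 5.2) cover signs as well as symptoms. If several comparisons in an adjusted family have real effects, some that Holm would declare may be missed under Bonferroni.

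**Working it through.** **1. The plan's own figure.** Inputs from section 13.1.1: difference 10, SD 20, two-sided alpha 0.05, power 80%, 10% drop-out.

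n per arm = 2 × (1.960 + 0.842)² × (20/10)² = 2 × 7.849 × 4 = 62.8, so 63.

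Adding 10%: 62.8 × 1.10 = 69.1, so 69 per arm and 138 in total, as stated. Dividing by 0.9 instead gives 63/0.9 = 70 per arm, or 140. Evaluable per arm after drop-out: 69 × 0.9 = 62.1, so about 62.

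**2. Why Holm cannot do worse.** Order the p-values in a family of m. Holm compares the k-th smallest with 0.05/(m − k + 1) and stops at the first failure.

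- Every Holm threshold is at least 0.05/m, so any p-value that passes Bonferroni also passes Holm.
- The first threshold is exactly 0.05/m, so the chance of at least one rejection is identical.
- If m₀ hypotheses are true nulls, the first of them to be rejected must meet a threshold no larger than 0.05/m₀. The union bound then gives a family-wise error of at most m₀ × 0.05/m₀ = 0.05, under any correlation.

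None of this depends on which family is chosen.

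**3. Thresholds.**

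| Family size | Bonferroni | Holm, in order of p-value |
|---|---|---|
| 3 | 0.0167 throughout | 0.0167, 0.025, 0.05 |
| 5 | 0.01 throughout | 0.01, 0.0125, 0.0167, 0.025, 0.05 |

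**4. Size of the gain if the family were the five secondary endpoints.** Assumptions, none of them from the documents: that family; one arm comparison per endpoint; correlation 0.3; effects as shown. The 0.5 SD is borrowed from the OSDI planning values (10/20).

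With 62 per arm, a 0.5 SD effect gives a z-statistic with mean 0.5 × √(62/2) = 2.784. Power per endpoint under Bonferroni is Φ(2.784 − 2.576) = Φ(0.208) = 58%. Holm was simulated with two-sided z-tests:

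| Real effects among five | Average power per real endpoint, Bonferroni | Holm |
|---|---|---|
| Five at 0.5 SD | 58% | 68–69% |
| Three at 0.5 SD | 58–59% | 62–63% |
| Two at 0.5 SD | 58–59% | 60–61% |
| One at 0.5 SD | 58–59% | 58–59% |
| Five at 0.3 SD | 18–19% | 21–22% |

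The ranges cover variation between simulation runs and, in some rows, 62 or 63 per arm. Using 63 per arm raises the 0.5 SD figures by about one point. With all five effects at 0.5 SD, the chance of declaring all five is 16–17% under Bonferroni and 39–40% under Holm. With three real effects and two nulls, family-wise error is about 2.0% and 3.5%, both below 5%. Holm lost no Bonferroni rejection in any run.

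**5. Size of the gain for three arm comparisons,** such as the three questionnaires, all assumed at 0.5 SD. Bonferroni: Φ(2.784 − 2.394) = Φ(0.390) = 65% per comparison. Holm: about 73–74% for correlations from 0.5 down to 0. These figures do not carry over to within-subject visit contrasts, where only the thresholds in step 3 apply.

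**The case against.** The strongest objection is that no family is defined. A reader might infer that the plan gives away power on the five tear-film endpoints, but section 6.1.7 only lists them and nothing says Bonferroni is applied across them. The text around the Bonferroni sentence reads at least as naturally as visit contrasts within each variable. This stands, and it makes every power figure above conditional.

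It also bears on the remedy. If the plan intends no adjustment across those endpoints, each arm comparison at 3 months would be tested at 0.05, with power Φ(2.784 − 1.960) = Φ(0.824), about 80%, at 0.5 SD. Imposing a five-endpoint Holm family would lower that to 68–69%. Confining the plan's only multiplicity sentence to those endpoints would also remove any adjustment of visit contrasts and of the three primary questionnaires. Three independent tests at 0.05 carry up to 1 − 0.95³ = 14% family-wise error. So the family should not be narrowed in the course of changing the method.

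Two further points stand. Bonferroni is valid and prespecified, and no stated figure changes. The largest gain, about 10 points, needs all five effects to be real at 0.5 SD; it is about 4 points with three, 2 with two and practically nothing with one.

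The objection does not reach the comparison of methods itself, which holds for any family of two or more tests.

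**Conclusion.** The point holds as a modest gain in efficiency, of low severity. For any family the sponsor intends, Holm matches Bonferroni's error control, retains all its rejections and can add to them. The gain under a five-endpoint family runs from essentially zero to about 10 points of average power per endpoint. It rests on an assumed family, assumed effects, correlation 0.3 and about 62 evaluable per arm.

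Three stronger readings are not supported:

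- That Bonferroni is an error. It controls the family-wise rate as intended.
- That real tear-film effects will be missed because of it. This is possible only if those endpoints are adjusted together and more than one comparison in the family is close to significance.
- That the five secondary endpoints are the trial's only objective evidence on signs. Section 11.1 also lists eyelid redness and swelling, bulbar redness, and corneal and conjunctival staining as efficacy parameters, and section 11.2 has them graded at the slit lamp at each visit.

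**What to change.** In the multiplicity sentence of section 13.1.3, name *Holm's step-down procedure* in place of Bonferroni's correction, and add that Holm-adjusted p-values will be reported. Leave the scope as the sponsor intends, whether visit contrasts, primary questionnaires, secondary endpoints or more than one of these. Do not restrict it to the five secondary endpoints. Holm needs a defined family just as Bonferroni does, so this change does not settle which comparisons are adjusted together; the sponsor still has to state that.

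The cost is a few words. The same p-values are used, the calculation can be done by hand, and no extra participants, visits or assumptions are needed. The one drawback is that simultaneous confidence intervals matching Holm's decisions are less simple than Bonferroni intervals.

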## 6. STUDY DESIGN

This study will be a prospective, randomised, placebo-controlled, double masked study conducted over a 3-month period.

One hundred and thirty-eight (138) participants who meet the inclusion / exclusion criteria and give informed consent will be randomised to either the test capsules containing a combination of flaxseed oil, borage oil and fish oil omega-3 fatty acids ("supplement") or placebo capsules, identical in appearance, containing non-active ingredients polyethylene glycol (500mg), oleic acid (659mg) and propylene glycol (115mg) to be taken by mouth three times daily for 40 days and then two times daily for the remainder of the study, as per the manufacturer's guidelines. Every effort will be made to stratify enrolment by disease severity to ensure participants with mild, moderate and severe dry eye are represented in the study population. Stratification will be in a 2:2:1 fashion i.e. OSDI score >12 (55 participants), OSDI score >20 (55 participants) and OSDI score >45 (28 participants). Participants will be stratified according to dry eye severity prior to randomisation.

There will be a total of 3 scheduled study visits over a period of approximately 3 months - Day 1, 1 month and 3 months. Ocular comfort and symptoms of dry eye will be assessed via questionnaires. The tear film and ocular surface will be assessed using specialised instruments (slit lamp biomicroscopy, Lipiview, Vapometer and Oculus Keratograph) and stains. Safety will be assessed through measurement of visual acuity, ocular redness (eyelid and bulbar conjunctival redness), evaluation of the ocular surface using the slit lamp biomicroscope and the administration of a questionnaire to assess general health and wellbeing.

In addition, at the first visit only, body mass index and body fat composition will be measured to investigate the potential relationship between nutrition, body composition, and dry eye (Ho et al, Eye Contact Lens; Epub ahead of print 27 May 2016).

All proposed procedures conform to the NHMRC Statement on Human Experimentation.

Participants are considered enrolled when they have signed the informed consent form and are regarded as part of the clinical trial population.

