### 6.1.2. Randomisation and Masking

Prior to initiation of study treatment, each subject who provides informed consent will be assigned to a subject number that will serve as the subject identification number on all study documents. Subject numbers will be assigned in ascending order and should not be omitted or reused.

Eligible subjects will be stratified according to dry eye severity (mild, moderate or severe) and then randomly assigned to 1 of the 2 study treatments. A randomization scheme will be prepared in advance.

Test and placebo capsules will be manufactured in accordance with local regulations including the TGA guidelines. All capsules will be identical in appearance as the outer capsule will be the same as the commercial test product. The manufacturer will code, bottle and label the test and placebo capsules to ensure that participants and investigators will be masked throughout the study duration. Both test and placebo capsules will have the same outer packaging and will be labelled as capsule "A" or "B". The code will be broken after completion of the study and data analysis, or if required for participant safety.

The recommended dosage will be 3 capsules per day by mouth to be taken with a meal for 40 days, and then 2 capsules per day thereafter for approximately 50 days, as per the manufacturer's guidelines.

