### 6.1.3. Clinical Trial Population

A total of 138 participants will be recruited for the study, which includes allowance for a 10% drop-out rate).

This sample size was calculated on the basis of detecting a difference in Ocular Surface Disease Index (OSDI) score of 10, with a standard deviation of 20, assuming an estimate of type 1 error  $\alpha = 0.05$  and power of 80% for a two tailed test. These values were obtained from Schiffman et. al. who demonstrated a mean difference in OSDI score of 10 between normal subjects and those with mild to moderate dry eye, with a standard deviation of up to 20.

Every effort will be made to stratify enrolment by disease severity to ensure participants with mild, moderate and severe dry eye are represented in the study population. Stratification will be in a 2:2:1 fashion i.e. OSDI score >12 (55 participants), OSDI score >20 (55 participants) and OSDI score >45 (28 participants).

Trial participants will be recruited from the local population at the investigational site. An e-mail invitation will be circulated to all SOVS staff, the Brien Holden Vision Institute, the Centre for Eye Health, SOVS post-graduate students, UNSW administrative staff and previous study participants who have indicated their willingness to be contacted to participate in future research studies. Advertisements may also be posted in University newsletters, notice boards, websites, local newspapers, social media (e.g. Facebook), on the SOVS clinic TV screen and other local advertising and community websites.

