## 7. SELECTION AND WITHDRAWAL OF PARTICIPANTS

### 7.1. Participant Selection

One hundred and thirty-eight (138) participants, both male and female, age 18 years and upwards who experience symptoms of ocular dryness will be enrolled into the study.

Every effort will be made to stratify enrolment by disease severity to ensure participants with mild, moderate and severe dry eye are represented in the study population. Stratification will be in a 2:2:1 fashion i.e. OSDI score >12 (55 participants), OSDI score >20 (55 participants) and OSDI score >45 (28 participants).

Informed consent will be obtained prior to any clinical trial procedures.

All participants will conform to the clinical trial entry criteria listed below:

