#### 7.1.1. Inclusion Criteria

- Able to read and comprehend English and give informed consent as demonstrated by signing a record of informed consent;
- Be at least 18 years old;
- Have symptoms of ocular discomfort as measured with the Ocular Surface Disease Index (OSDI) score of >12 at the Baseline visit;
- Willing to comply with the dosage and study visit schedule as directed by the investigator;
- No contact lens wear in the last 30 days and willing to refrain from contact lens wear for the duration of the study;
- No planned changes to diet and willing not to substantially alter their usual diet for the duration of the study, including their typical intake of fish;
- Willingness to notify the study investigator if instructed to alter their diet by health/medical practitioner;
- Willing to continue using any artificial tear supplements at the same frequency throughout the study, as used prior to the study;
- Have health and ocular health findings which would not prevent the participant from safely ingesting dietary supplementation with combination omega oils.

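### Participants are stratified on baseline OSDI, but no listed test adjusts the between-group comparison for baseline OSDI or stratum, so precision is given up

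*Combined protocol and SAP*

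**What the plan says.** **Design.** Section 6 states: "Participants will be stratified according to dry eye severity prior to randomisation". Section 6.1.2 repeats it ("Eligible subjects will be stratified according to dry eye severity (mild, moderate or severe) and then randomly assigned") and adds "A randomization scheme will be prepared in advance", without saying whether arms are balanced within strata. The strata are OSDI bands; section 7.1 gives the quotas: "Stratification will be in a 2:2:1 fashion i.e. OSDI score >12 (55 participants), OSDI score >20 (55 participants) and OSDI score >45 (28 participants".

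**Baseline data.** OSDI is an entry criterion in section 7.1.1 ("Have symptoms of ocular discomfort as measured with the Ocular Surface Disease Index (OSDI) score of >12 at the Baseline visit"), so every eligible participant has a baseline score. Table 4 schedules the comfort questionnaires at all three visits.

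**Analysis.** Section 13.1.3 offers a menu: "Commonly used tests of significance at each visit may include paired t-tests and group t-test for parametric data", signed rank and rank sum tests for non-parametric data, or "repeated measures Analysis of Variance (ANOVA) for parametric data to determine differences between within-subject factors". Friedman, McNemar and chi-square tests complete the list. Section 13 contains no ANCOVA, no baseline-adjusted mixed model and no stratified test.

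**Sample size.** Section 13.1.1 uses an OSDI difference of 10, an SD of 20, two-sided 5% and 80% power, giving 138 participants (69 per arm) with a 10% drop-out allowance.

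**The concern.** Baseline score is usually informative about the follow-up score, and here the design already treats it as important enough to stratify on. The listed tests do not use it to sharpen the comparison of arms:

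- The group t-test and rank sum test have no baseline or stratum term.
- The paired tests work within a group.
- The repeated measures ANOVA is described for within-subject factors. With a group-by-visit term added on baseline and 3 months, it is the change-score test.
- The hypothesis in section 5.2 is worded as a greater reduction, which may also point to a change score.

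A change score uses the baseline but does not adjust for it. It fixes the baseline coefficient at 1, and at low correlation that is worse than ignoring baseline. What is at stake is power and the width of the confidence interval, not the validity of the test.

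**Working it through.** **Inputs from the documents (13.1.1, 13.1.2):** difference 10, SD 20, two-sided 5%, power 80%, 69 per arm, 10% drop-out. **Assumed, because the documents do not give it:** the baseline-to-3-month correlation r, taken as 0.3, 0.5 and 0.7.

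**Step 1: reproduce the plan's figure.** n per arm = 2(1.960 + 0.842)² × 20² / 10² = 62.8, so 63. Then 63 × 1.1 = 69.3, which is 69 per arm or 138 in total if rounded down (63/0.9 = 70 gives 140). The 138 therefore comes from an unadjusted two-group comparison. Evaluable: 69 × 0.9 = 62.1, so 62 per arm.

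**Step 2: unadjusted 3-month test.** SE = 20√(2/62) = 3.59. Power = Φ(10/3.59 − 1.96) = 79.5% (78.9% with the t-distribution).

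**Step 3: closed form for ANCOVA.** Residual SD = 20√(1 − r²).

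| r | Residual SD | Power, 62 per arm | Difference detectable at 80% power |
|---|---|---|---|
| 0 (unadjusted) | 20.0 | 79.5% | 10.1 |
| 0.3 | 19.1 | 83.1% | 9.6 |
| 0.5 | 17.3 | 89.5% | 8.7 |
| 0.7 | 14.3 | 97.4% | 7.2 |

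**Step 4: simulation of the stratified design.** 20,000 trials per cell. Strata of 50/50/24 (the quotas less about 10%), with baseline assumed uniform on 12-20, 20-45 and 45-80. The stratum means are 16, 32.5 and 62.5, so the between-stratum variance is 283.3 and the within-stratum variance 42.9. Baseline SD = √326.2 = 18.1, and the strata carry 283.3/326.2 = 87% of the variance. Power at SD 20:

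| Allocation | r | 3-month t-test | Change score | ANCOVA | Gain over 3-month test | Gain over better option |
|---|---|---|---|---|---|---|
| Balanced within strata | 0 | 78.9% | 54.2% | 78.5% | −0.4 | −0.4 |
| | 0.3 | 79.7% | 71.0% | 82.0% | 2.3 | 2.3 |
| | 0.5 | 81.6% | 84.3% | 88.6% | 7.0 | 4.3 |
| | 0.7 | 85.1% | 96.6% | 97.1% | 12.0 | 0.5 |
| Not balanced | 0 | 78.8% | 53.1% | 77.7% | −1.1 | −1.1 |
| | 0.3 | 79.1% | 68.9% | 82.0% | 2.9 | 2.9 |
| | 0.5 | 78.8% | 82.3% | 88.5% | 9.7 | 6.2 |
| | 0.7 | 78.8% | 96.0% | 96.8% | 18.0 | 0.8 |

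The change-score column agrees with its formula, SD = √(20² + 18.06² − 2r × 20 × 18.06) = 22.6/19.1/14.9, which gives power 69/83/96% at r = 0.3/0.5/0.7. The change score overtakes the 3-month score once r exceeds 18.06/(2 × 20) = 0.45.

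**Step 5: type I error.** With balance within strata, the unadjusted t-test counts between-stratum variation in its standard error although the design has removed it from the comparison. True error = 2[1 − Φ(1.96/√(1 − 0.87r²))] = 4.1/2.7/1.0%; simulated 4.0/2.8/1.0%. Without balance it is about 5%. ANCOVA is about 5% either way.

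**Step 6: smaller SD.** Section 13.1.1 describes 20 as an upper value, so lower SDs were assumed (balanced, 10,000 trials per cell), again for r = 0.3/0.5/0.7:

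| SD | 3-month t-test | Change score | ANCOVA |
|---|---|---|---|
| 18 | 87/89/93% | 77/89/98% | 89/94/99% |
| 16 | 94/95/98% | 83/93/99% | 95/98/99.8% |

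The gain over the better option is then 2/5/0.6 points at SD 18 and 1/2/0.5 at SD 16.

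**Step 7: the stratum term.** Leaving it out while keeping continuous baseline changed ANCOVA power by 0 to 0.7 points, in favour of the smaller model.

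**The case against.** - **The menu is permissive.** Section 13.1.3 uses the word may, so ANCOVA is not forbidden, and the larger gap is that no primary analysis is fixed. This is fair, but an adjusted model chosen after the data are seen would not be pre-specified.
- **The gain is small against the better unadjusted option:** about 2/4/0.5 points at SD 20. This stands. However, the better option depends on r, which is unknown. On the balanced figures, choosing wrongly costs about 9 points at r = 0.3 (79.7 − 71.0) or 12 at r = 0.7 (96.6 − 85.1) relative to the other unadjusted test.
- **The simulation is idealised.** About 40% of participants enter with OSDI between 12 and 20 on a scale that stops at 0, and about 9% of simulated 3-month scores were negative. With scores floored at 0 and benefit proportional to baseline, the gain falls to about 0/3/6 points over the 3-month test and about 0/3/2 over the better option. ANCOVA was never worse beyond simulation error, so the direction holds but the size is less firm.
- **The trial is adequately powered as it stands.** True, and no bias or underpowering is alleged.
- **Secondary outcomes are less simple.** Section 11.2 takes break-up time and evaporation per eye and in triplicate, so an eye and averaging rule is needed before ANCOVA can be applied. This stands for the tear-film measures and does not affect OSDI.

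**Conclusion.** The concern holds. The plan stratifies on baseline OSDI and then lists no analysis that adjusts for it. The cost is lost efficiency. At SD 20 with balance within strata, ANCOVA adds about 2/7/12 points of power over the 3-month t-test and about 2/4/0.5 over the better unadjusted test, for assumed r = 0.3/0.5/0.7. At r = 0 it costs at most about 1 point. It was at or above both alternatives at every non-zero r in the main simulations. The gain shrinks at lower SD and under flooring with proportional benefit. The conservative type I error of the unadjusted test (about 4/3/1%) applies only if arms are balanced within strata, which section 6.1.2 does not state. The gain for OCI, DEQ-5 and the tear-film measures was not quantified. This is a recommended improvement, not a flaw that invalidates the trial.

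**What to change.** In section 13.1.3, specify that the between-group comparison of 3-month OSDI uses ANCOVA (or an equivalent mixed model) with treatment, continuous baseline OSDI and the severity stratum used in randomisation. Report the adjusted mean difference with its 95% CI. Say that the stratum term is there to match the design; it brings no extra power. Treat the other continuous outcomes in the same way, each with its own baseline, after stating how eyes and repeat readings are combined for the tear-film measures.

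For OSDI the cost is wording only: baseline score and stratum are already recorded for everyone randomised, and the sample size need not change. Which scale and time point are primary is a separate decision.

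### Section 13.1.3 sends ranked variables to within-subject tests by rule, while between-arm tests are only optional and none is tied to a deciding questionnaire or visit

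*Combined protocol and SAP*

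**What the plan says.** The clinical hypothesis (Section 5.2) is a greater reduction in discomfort and/or signs of dry eye on supplement than on placebo over 3 months. Section 13.1.1 sizes the trial at "69 in each group" on the basis of "detecting a difference in OSDI score of 10, with a standard deviation of 20".

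Section 13.1.3 then does five things:

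- It gives the aim of testing as finding significant differences between visits. A word in that sentence is doubled, so a second term may have dropped out, but no other sentence states a supplement-versus-placebo aim.
- It offers a list of options: "Commonly used tests of significance at each visit may include paired t-tests and group t-test for parametric data". Where data are not parametric, the same list offers the signed-rank and rank-sum tests in their place.
- It adds repeated-measures ANOVA for parametric data, "to determine differences between within-subject factors".
- It states as a rule: "Ranked variables will be analysed non-parametrically using Friedman's analysis of variance or Wilcoxon Signed Rank test to determine differences".
- It states as a further rule that "grouped categorical variables will be analysed using Chi-Square tests".

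The Synopsis names three questionnaires (OSDI, OCI, DEQ-5) as the primary efficacy variable without ranking them. Section 6.1.6 refers only to validated questionnaires. Neither names a visit.

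**The concern.** Friedman's test and the signed-rank test compare visits within participants; neither uses treatment arm. Applied to a graded sign, they can show that the grade moved during the study. They cannot show that it moved differently on supplement and placebo.

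The variables most likely to be affected are the redness and staining grades, scored 0-4 (Section 11.2, Appendices III and IV). They are primary safety variables in the Synopsis, they are also efficacy parameters in Section 11.1, and signs of dry eye are part of the hypothesis. If the ranked rule were followed literally, neither the efficacy question nor the safety question for these grades would be answered by a comparison with placebo.

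For the symptom scores the gap is different. A suitable test is available but not assigned. With three questionnaires, two follow-up visits and a Bonferroni correction whose family is undefined, the plan does not say which result decides the trial or at what significance level.

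**Working it through.** **1. What the sample size assumes.** Inputs from Section 13.1.1: difference 10, SD 20, two-sided alpha 0.05, power 80%, 10% drop-out.

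- Two-sample: n = 2 × (1.960 + 0.842)² × (20/10)² = 62.8 per arm; 62.8 × 1.10 = 69.1, the stated 69.
- Paired, treating 20 as the SD of change (an assumption): n = (1.960 + 0.842)² × (20/10)² = 31.4; × 1.10 = 34.5.

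The stated figure is that of a between-arm comparison.

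**2. Which listed procedures compare the arms.**

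| Procedure in Section 13.1.3 | Status | Compares arms? |
|---|---|---|
| Paired t-test, signed-rank | option | no |
| Group t-test, rank-sum | option, at each visit | yes, on the natural reading |
| Repeated-measures ANOVA | option, aimed at within-subject factors | not as described |
| Friedman or signed-rank for ranked variables | rule | no |
| Chi-Square for grouped categorical variables | rule | yes |

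Only Chi-Square is both firm and between-arm.

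**3. What the ranked rule can miss.** Hypothetical counts, not from the documents: 62 completers per arm; of all 124, 48 improve one grade, 16 worsen one grade and 60 are unchanged. With one-grade changes the signed-rank statistic is z = (improved − worsened)/√(improved + worsened).

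- Arms pooled: z = 32/√64 = 4.0, p = 0.00006, however the counts divide between arms.
- Arms identical, 24 improved and 8 worsened in each: rank-sum on change gives p = 1.0.
- Arms different, 34/6 versus 14/10: rank-sum on change gives z = 3.39, p = 0.0007.
- Signed-rank run separately in those last two arms: z = 28/√40 = 4.43, p = 0.00001; and z = 4/√24 = 0.82, p = 0.41.

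The pooled p-value does not distinguish the second case from the third. The separate p-values do react to the split, but two within-arm p-values are not a test of the difference. To illustrate, suppose both arms have the same true standardised change, with 62 per arm and a paired t-test in each. The chance of significance on supplement but not on placebo is 4.8% at a change of 0, 22.5% at 0.2 and 25.0% at 0.25.

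**4. What is at stake for the primary comparison.** Completers: 69 × 0.90 = 62.1, taken as 62 per arm. Two-sample t-test with noncentrality (10/20) × √(62/2) = 2.784 on 122 degrees of freedom:

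| Comparisons under Bonferroni | Alpha | Power |
|---|---|---|
| 1 (one questionnaire, one visit) | 0.05 | 78.9% |
| 2 (one questionnaire, two visits) | 0.025 | 69.6% |
| 6 (three questionnaires, two visits) | 0.0083 | 54.2% |

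For two comparisons, 80% power would need 78 completers per arm. The families of two and six are assumptions, because Section 13.1.3 defines none.

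**The case against.** The best reply is that the sentences of Section 13.1.3 are meant to be read together: group t-test or rank-sum between arms at each visit, and repeated-measures ANOVA or its non-parametric counterpart, Friedman, across visits. On that reading they complement each other, and the rank-sum test already serves ranked data. The reading is open and reasonable. It does not settle the matter, because the rank-sum test is something the analysis may include, whereas the ranked-variable sentence says what will be done.

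Second, the reach of the ranked rule is inferred. The plan never says that the grades are ranked, and they could be handled as grouped categorical variables by Chi-Square, which compares arms. The five secondary endpoints in Section 6.1.7 are instrument measurements, not grades. This stands: the rule's likely reach is the graded signs, not the main efficacy variables.

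Third, the power losses measure an unspecified multiplicity family, not the choice of test. That also stands, and is why they are given as conditional figures.

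A reader might go further and infer that the plan has no between-arm test, or that OSDI will be judged within subjects. The documents do not support either. Between-arm tests are listed, and Section 13.1 treats interval variables with a large enough sample as normal, which points OSDI to the group t-test.

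**Conclusion.** The point holds as a gap in specification that should be closed before analysis. The hypothesis and sample size are between-arm; the stated testing aim, the ANOVA target and the firm rule for ranked variables are not. Variables treated as ranked have no firm between-arm test, and the primary endpoint has no named deciding questionnaire or visit.

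Its size depends on assumptions. Power is 78.9% with one named comparison, and 69.6% or 54.2% under the two assumed Bonferroni families, all with 62 completers per arm and SD 20 for whatever score is analysed. The worked grades use invented counts. Their invariance to arm applies only if the arms are pooled, which the plan does not state.

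Nor does the text show that tests would be chosen to favour the supplement. Section 6.1.2 keeps the code closed until the analysis is complete, apart from participant safety. The problem is that the ranked rule, taken literally, answers a different question from the one posed.

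**What to change.** 1. In Section 13.1.3, state that the inferential comparison for every efficacy variable and graded sign is supplement versus placebo. Say how the 0-4 grades are classified. Replace Friedman and signed-rank as their inferential test with the rank-sum test already listed, applied to change from baseline to a named scheduled visit. Keep unscheduled-visit data for adverse-response analysis, consistent with Section 13.3 and with the rule that "The analysis of safety variables such as adverse responses will include all visits, including all unscheduled visits". Keep the Chi-Square rule.
2. Name one primary comparison. An example is change in OSDI, the sizing variable, from baseline to 3 months by the group t-test, or the arm-by-visit contrast at 3 months if repeated-measures ANOVA is kept. The 3-month visit is inferred from the period in the hypothesis. State whether change or visit score is analysed: the SD of 20 comes from a comparison of normal and dry-eye subjects, and the plan gives no SD of change. Make the Synopsis and Section 6.1.6 agree, with OCI and DEQ-5 as secondary.
3. Do not let within-arm comparisons between visits support a claim of difference from placebo.

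The cost is wording in the Synopsis, Section 6.1.6 and Section 13.1.3, and the loss of co-primary standing for OCI and DEQ-5. No new data, visits or participants are needed.
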